10.2 Sample size calculation

A two-stage Green-Dahlberg design has been used [Green SJ and Dahlberg S Statistics in Medicine 11:853-862,1992], to calculate the sample size for the **P-cohort** under the following assumptions:

- The null hypothesis that the true (H_0) response rate is 10% (not considered clinically compelling) will be tested against a one-sided alternative (H_1).
- In the first stage, 10 patients will be accrued. If no responses are observed, the study will be stopped. Otherwise, 10 additional patients will be accrued for a total of 20.
- The null hypothesis will be rejected if 5 or more responses are observed in 20 patients.
- This design yields a type I error rate of .05, and power of 90% when the true response rate is 40%.
- In order to recruit 20 patients in the P-cohort the number of MMR unselected patients to be pre-screened for MMR status MGMT promoter methylation and the number of MGMT-PM+ to be primed with TMZ are reported in Table 10.1. below as well as in Study Diagram, section 4.2.

Table 10.1 Number of patients required in each trial Phase.

Number of Patients to be:	N	Expected Percent
RAS mut MMR proficient cases to be screened	670	A
expected MGMT IHC negative	335	B = 50% of A
expected promoter methylated in tissue	67	C=20% of B and 10% of A
expected with increase of mutational load ≥ 20 mutations/Mb (PRIMING Phase)	20	D= 30% of C

For cohort D, a precise sample size has NOT been calculated since the ORR in deficient patients is a secondary objective of the trial. We will enroll up to 34 MMR-D cases according to an estimated prevalence of 4-5 %. These patients will constitute the **D-cohort**. We expect a response rate between 40% (95% C.I. .18-.71) and 33% (95% C.I. .21-.46) as reported by Le et al., (2015 & 2019) with 11-14 responses accordingly.

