10.3 Statistical Analysis Plan

10.3.1 Populations considered for the analysis

All patients signing the informed consent for the PRIMING and TRIAL Phases will be accounted for. The number of patients who will not result eligible, who died or withdrew before these phases, will be specified.

A patient will be considered to be PRIMING and TRIAL Phases eligible if he/she did not have any deviation from the patient entry criteria listed in section 7.1.2 (PRIMING) and 7.1.3 (TRIAL). Potential eligibility problems will be assessed by the Clinical Study Coordinator at time of medical review.

The final efficacy analysis will occur after 20 patients entered in the P-Cohort are evaluable for response according to RECIST 1.1. The distribution of follow-up time in both cohorts (P and D) will be described and the number of patients lost to follow-up will be reported.

Conclusions will be based on all eligible patients in each cohort. Further analysis may be performed excluding those patients for whom major protocol deviations have been identified (e.g., early death due to other reasons, early discontinuation of treatment, major protocol violations, etc.). However, these sub-analyses may not serve as the basis for drawing conclusions concerning treatment efficacy, and the reasons for excluding patients from the analysis should be clearly reported.

Three populations will be considered for the analysis, as follows:

- The Safety Evaluable (SE) population defined as all treated patients (i.e. eligible as decided at the time of registration that receives at least 1 dose of any study treatment i.e. TMZ and Pembrolizumab). An incorrect treatment schedule or drug administration or an early termination of treatment does not result in exclusion of patients from this population. This population will be the object of the Safety and Tolerability analysis. Patients with major deviations from the eligibility criteria affecting safety or from the treatment schedule at cycle 1 for reasons other than toxicity may be presented in separate tables/listings.
- The Efficacy Evaluable (EE) population defined as all patient treated with pembrolizumab in P-cohort, with no major deviations from the eligibility criteria affecting efficacy evaluation, for which the tumor response could be evaluated at least once while on treatment. These patients should have received at least 2 cycles after treatment starts, unless disease progression occurs within this period.

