10.3.2 Primary analysis

The main analysis will focus on the objective response rate (ORR) of the P Cohort.

An objective response is defined as either a CR or PR assessed, as outlined in sections 9.1.3 and 10.3.1 (iEE population), first by RECIST 1.1 and then by iRECIST criteria at the discretion of the local Investigator.

Best objective response of either type will be centrally confirmed using the [Quibim Precision[®]](#) software (the cloud-based repository for radioimaging). In case of disagreement between local and central evaluation, the central response evaluation will be used for the analysis. The duration of response will be calculated accordingly.

An estimate of ORR and its 95% CIs will be calculated using the Clopper-Pearson method. Discrepant results, impinging in the acceptance of rejection of the null hypothesis, will be discussed and agreed upon between the Protocol Chair and the Sponsor.

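### Section 10.3.2 lets the Protocol Chair and the Sponsor settle undefined discrepancies about the null hypothesis by agreement, which can override the fixed 5-of-20 rule

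*Combined protocol and SAP*

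**What the plan says.** **The test.** Section 10.2 sets a null response rate of 10% that "will be tested against a one-sided alternative". Cohort P stops if none of the first 10 patients responds. Otherwise, "The null hypothesis will be rejected if 5 or more responses are observed in 20 patients".

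**The read.** Section 10.3.2 says: "In case of disagreement between local and central evaluation, the central response evaluation will be used for the analysis". Section 9.1.3.1 plans this central review for trial end, by two radiologists reading blinded, with the review protocol and reconciliation report made available.

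**The interval.** Section 10.3.2: "An estimate of ORR and its 95% CIs will be calculated using the Clopper-Pearson method".

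**The clause.** The next sentence, which closes section 10.3.2, is: "Discrepant results, impinging in the acceptance of rejection of the null hypothesis, will be discussed and agreed upon between the Protocol Chair and the Sponsor".

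**The set.** Section 10.3.1 contains three statements that bear on who is counted: "The final efficacy analysis will occur after 20 patients entered in the P-Cohort are evaluable for response according to RECIST 1.1"; "Conclusions will be based on all eligible patients in each cohort"; and, for analyses that drop patients with major deviations, "these sub-analyses may not serve as the basis for drawing conclusions concerning treatment efficacy".

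**The concern.** A two-stage rule has a known error rate because nobody chooses the verdict after seeing the count. The closing clause of section 10.3.2 reintroduces that choice. It applies only when the null hypothesis is at stake, and it does not say what may trigger it, what standard applies, or that anyone outside the study leadership takes part. The timing is not written, but a discrepancy that bears on the null hypothesis can be seen only when results exist.

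The trial is open-label and single-arm, and its verdict turns on one response in 20. A verdict settled by agreement could be challenged whichever way it went. The exposure is larger because the plan leaves more than one count that could be called the primary result.

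**Working it through.** **1. The plan's own rule.** Inputs from section 10.2: n1 = 10, n2 = 10, stop at 0 of 10, reject at r = 5 or more of 20, null 10%, alternative 40%. With X1 and X2 the responses in each stage:

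P(reject) = P(X1 + X2 ≥ r) − P(X1 = 0) × P(X2 ≥ r)

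- At 10%: 0.0432 − 0.3487 × 0.0016 = 0.0426.
- At 40%: 0.9490 − 0.0060 × 0.3669 = 0.9468.

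The plan states 0.05 and 90%. The exact values differ, but both on the safe side. Left alone, the rule does what is asked of it.

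**2. How much one response matters.** The same formula with other cut-offs:

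| Reject at | Type I error (10%) | Power (40%) |
|---|---|---|
| 4 or more | 0.128 | 0.980 |
| 5 or more (plan) | 0.043 | 0.947 |
| 6 or more | 0.011 | 0.873 |

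**3. Where two counts can arise.**

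*Read.* Suppose there are 5 local and 4 central responses. The central-read rule gives 4 of 20, so the null stands. This is also a discrepancy that bears on the null hypothesis, so the closing clause appears to send it to agreement. Section 10.3.2 does not say which sentence yields.

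*Criterion.* The passages point two ways:

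- Towards RECIST 1.1: section 9.1.3.2 makes it the primary measure of response; section 10.3.1 uses it to trigger the final analysis and describes the iEE analysis as a second one.
- Towards RECIST followed by iRECIST: section 10.1 ties the main analysis to iEE. Section 10.3.2 applies RECIST 1.1 and then iRECIST at the local investigator's discretion, and refers to best response of either type. The primary endpoint (Synopsis and section 5.4) cites Table 9.1.3, which contains the iRECIST step. Appendix 4 says there is no separate iRECIST assessment before RECIST progression.

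Four RECIST responders plus one patient who responds after an initial RECIST progression make 4 of 20 on one reading and 5 of 20 on the other.

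*Set.* Section 10.1 requires at least 1 cycle and calls this iEE. Section 10.3.1 refers to 20 evaluable patients, to all eligible patients, and to EE. EE requires an on-treatment response evaluation and normally at least 2 cycles, and iEE is then said to be the same population as EE. A patient who leaves after one cycle without a scan counts under section 10.1 but not under EE. If the patient who takes that place among the 20 evaluable is the fifth responder, the sets give 4 of 20 and 5 of 20.

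**4. Rule beside interval.** Clopper-Pearson limits for x of n are the α/2 quantile of Beta(x, n − x + 1) and the 1 − α/2 quantile of Beta(x + 1, n − x). The plan does not state the sidedness; two-sided is assumed.

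| Responses | 95% interval | 90% interval | 5-of-20 rule |
|---|---|---|---|
| 4/20 | 5.7–43.7% | 7.1–40.1% | not rejected |
| 5/20 | 8.7–49.1% | 10.4–45.6% | rejected |
| 6/20 | 11.9–54.3% | 14.0–50.8% | rejected |

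The 95% interval and the rule part company only at 5/20. The single-stage one-sided exact p there is 0.043: below 0.05, which the rule uses, and above 0.025, which each side of a 95% interval uses. The 90% interval agrees with the rule throughout the table.

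**The case against.** **The clause may concern only local against central reading.** That is its most natural target, and the central review has real safeguards: two blinded readers and a reconciliation report. But section 10.3.2 already says the central read is used. If the clause covers only that case, it is either redundant or it displaces the central read exactly when the null hypothesis is at stake. Either way it should go.

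**The criterion may not be open.** Section 5.4, Table 9.1.3, section 10.3.2 and Appendix 4 fairly support a sequential composite in which either type of response counts. This stands in part: it is a coherent reading. It still has to be reconciled with section 9.1.3.2 and with the description of iEE as a second analysis in section 10.3.1.

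**Some conflicts are already closed.** Analyses that exclude major deviations cannot carry the conclusion. This stands, and nothing expressly links the clause to the choice among the remaining sets.

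**Rule and interval at 5/20.** A reader might infer that the plan contradicts itself there, rejecting the null by one route and not by the other. The documents do not support this. Section 10.2 gives the only test, and section 10.3.2 gives the interval an estimation role. A one-sided 5% rule reported beside a two-sided 95% interval is a matter of presentation. It matters here only because an undefined clause follows it directly.

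**Conclusion.** The concern holds in this form: an undefined, criterion-free agreement stands above a fixed decision rule, and the plan does not name one criterion and one set for that rule. It should be corrected before the data are analysed. The design itself is sound, with exact type I error 0.043 and power 0.947 at 40%.

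A one-response shift would move type I error to 0.128 or 0.011, the latter with power 0.873 against the stated 90%. A reader might take 0.128 as the trial's actual or worst-case error rate. The documents do not support that. They do not say that 4/20 would be called positive, and at 4/20 the rule and the 95% interval agree on not rejecting. The figures only show how much rests on a single response.

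Assumptions: the null and alternative rates of section 10.2; independent responses; 20 patients; the same read and criterion at both stages. The Clopper-Pearson limits ignore the two-stage design. That the agreement follows sight of the results is an inference from the wording. Nothing in the documents suggests an intent to steer the result.

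**What to change.** 1. Delete the closing sentence of section 10.3.2.
2. State in its place that the null hypothesis is rejected if and only if 5 or more of 20 cohort P patients respond on the central read, by one named criterion and in one named analysis set.
3. Have the sponsor name the criterion and the set before the data are analysed, and make sections 10.1, 10.3.1 and 10.3.2 agree with that choice and with section 9.1.3.2.
4. State that every other criterion, read and set is a sensitivity analysis that cannot change the verdict.
5. As a minor point of presentation, label the two-sided 95% Clopper-Pearson interval descriptive, or add a two-sided 90% interval, which matches the one-sided rule.

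The cost is wording, and the sponsor gives up discretion over the verdict. If RECIST 1.1 alone is named, responses after an initial RECIST progression would count only in a sensitivity analysis. If a set other than the 20 evaluable patients is named, the trigger for the final analysis in section 10.3.1 must be reworded to match.

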10.3.3 Secondary analyses

A secondary analysis will also estimate the ORR, as defined above, in the D-Cohort and compare it to the ORR in the P-cohort. CIs for the difference in ORRs between the two cohorts

will be determined using the normal approximation to the binomial distribution. The ORRs will be compared between the two cohorts with use of the stratified Cochran-Mantel-Haenszel test.

PFS and OS, for both cohorts, will be estimated using the Kaplan-Meier product-limit method. Estimates at weekly intervals will be tabulated with their standard error; medians will be provided with 95% confidence interval.

DCR is defined as the rate of patients with complete or partial response as best response or stable disease maintained for ≥ 18 weeks per RECIST v1.1. The analysis methods for DCR will be the same as those for the analysis of ORR.

Duration of response, defined as the time between the date of the first occurrence of a complete or partial response and the date of first documented progressive disease or death is documented, will also be estimated using Kaplan-Meier methodology above. Patients who have not progressed or who have not died by the data cutoff date for analysis will be censored at the time of last tumor assessment date. If no tumor assessments were performed after date of the first occurrence of a complete or partial response, DOR will be censored at the date of the first occurrence of a complete or partial response plus 1 day.

Adverse events will reported as proportions.

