7.5 Stratification

For exploratory analysis purpose only, patients will be stratified post-hoc according to selected immune biomarkers (see 9.1.4.2) or other putative predictive markers.

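### The normal-approximation interval for the P-versus-D difference in ORR can be too narrow, if it is reported after a 0/10 stop or if cohort D stays small; a score interval should replace it (minor)

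*Combined protocol and SAP*

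**What the plan says.** Section 10.3.3 plans to estimate the ORR in cohort D and compare it with cohort P. Intervals for the difference "will be determined using the normal approximation to the binomial distribution". The section states neither the confidence level, nor pooled or unpooled variance, nor any continuity correction. It adds: "The ORRs will be compared between the two cohorts with use of the stratified Cochran-Mantel-Haenszel test". For disease control rate (DCR): "The analysis methods for DCR will be the same as those for the analysis of ORR".

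Four other places bear on this:

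- Section 10.2 accrues 10 P patients first: "If no responses are observed, the study will be stopped". Otherwise accrual goes to 20. For cohort D: "We will enroll up to 34 MMR-D cases", with 11 to 14 responses expected.
- Section 10.3.1 gives the timing: "The final efficacy analysis will occur after 20 patients entered in the P-Cohort are evaluable for response according to RECIST 1.1". It describes no analysis after a first-stage stop.
- Section 10.3.2 uses an exact method for the single-cohort rate: "An estimate of ORR and its 95% CIs will be calculated using the Clopper-Pearson method".
- Section 7.5 is the only section on stratification: "For exploratory analysis purpose only, patients will be stratified post-hoc according to selected immune biomarkers". It assigns nothing to the Cochran-Mantel-Haenszel (CMH) test.

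**The concern.** The unpooled Wald interval takes each cohort's variance from its observed proportion. It is unreliable with small samples and low counts, and it breaks down at a count of zero. A count of 0/10 is cohort P's own stopping outcome. The plan uses an exact interval for P's rate but gives no similar protection to the difference.

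Section 4.1 presents cohort D as the positive reference for cohort P. If priming fails, readers will want to see P set against D. At 0/10 the interval would treat P's rate as known to be exactly zero, although the Clopper-Pearson interval for the same data reaches 30.8%. At stake is the stated precision of a secondary, non-randomised contrast.

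**Working it through.** **Inputs.** From 10.2: 10 P patients, stop at 0/10, otherwise 20; reject at 5 or more responses; P rates of 10% and 40%; D at most 34, with rates of 33% to 40%. Assumed, because the plan does not say: two-sided 95% level, unpooled variance, no continuity correction. Differences below are D minus P.

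**The plan's own figures.** Summing P(X1 = x)·P(X2 ≥ 5 − x) over x = 1 to 10 gives a type I error of 0.0426 at 10% and power of 0.947 at 40%. Both are consistent with the stated .05 and 90% read as limits. Expected D responses: 34 × 0.33 = 11.2 and 34 × 0.40 = 13.6, matching 11 to 14.

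**Probability of a 0/10 stop**, (1 − p)^10: 34.9% at p = 10%, 10.7% at 20%, 0.6% at 40%.

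**The interval at 0/10.** SE² = pD(1 − pD)/nD + pP(1 − pP)/nP, and the P term is 0 × 1/10 = 0. For 11/34, SE = √(0.3235 × 0.6765/34) = 0.0802, and 32.4% ± 1.96 × 8.02 gives +16.6% to +48.1%. That is cohort D's own Wald interval. The Clopper-Pearson upper limit for 0/10 is 1 − 0.025^(1/10) = 30.8%.

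| D against P | Wald | Miettinen-Nurminen |
|---|---|---|
| 11/34 vs 0/10 | +16.6% to +48.1% | +2.1% to +49.4% |
| 14/34 vs 0/10 | +24.6% to +57.7% | +10.6% to +58.0% |
| 10/34 vs 0/10 | +14.1% to +44.7% | −0.7% to +46.4% |
| 11/34 vs 2/20 | +1.9% to +42.9% | includes zero |

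**One-stratum CMH test**, χ² = (x − E)²/V with hypergeometric V, where x is the P count:

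- 11/34 vs 0/10: E = 10 × 11/44 = 2.5; V = 10 × 34 × 11 × 33/(44² × 43) = 1.483; χ² = 4.22, p = 0.040.
- 14/34 vs 0/10: E = 3.18, V = 1.715, χ² = 5.90, p = 0.015.
- 10/34 vs 0/10: p = 0.054.
- 11/34 vs 2/20: p = 0.066.

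So Wald and CMH agree at 0/10 for the expected D counts. They conflict there at 4 to 10 D responses of 34.

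**Coverage with the stop path counted, D = 34.** All outcomes were enumerated exactly, assuming that the comparison is also reported after a stop. Each cell is Wald / Miettinen-Nurminen.

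| P rate | D 33% | D 40% |
|---|---|---|
| 10% | 89.7 / 97.0 | 88.1 / 97.0 |
| 20% | 88.0 / 95.0 | 88.9 / 95.4 |
| 25% | 89.7 / 94.8 | 90.3 / 94.6 |
| 30% | 91.4 / 93.9 | 91.7 / 94.3 |
| 40% | 93.3 / 95.0 | 93.6 / 94.1 |

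Newcombe's score interval, run at P rates of 10%, 20% and 40%, covers 94.1% to 96.9%.

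**Coverage given that P reaches 20.** At D = 34, over the same grid, Wald covers 93.8% to 95.4% and Miettinen-Nurminen 94.6% to 95.9%. At D = 10 (an illustrative size), D rate 33% and P rate 10%, Wald covers 88.4% and Miettinen-Nurminen 96.8%.

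**Smaller D, stop path counted.** Across D = 10, 17, 20 and 25, Wald covers 88.7% to 93.8% and Miettinen-Nurminen 93.6% to 97.4%.

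**The case against.** The strongest objection is that the shortfall at D = 34 belongs to an analysis that the plan does not schedule. Section 10.3.1 ties the final efficacy analysis to 20 evaluable P patients, 10.2 says only that the study stops, and 34 is a maximum that cohort D may not reach. With 20 and 34 patients Wald is close to nominal. This stands, and it limits the point. It does not remove it: nothing in 10.3.3 excludes the comparison after a stop, and a small cohort D can cause under-coverage even with 20 P patients.

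Four stronger readings are tempting, and the documents do not support them:

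- *That the plan necessarily gives cohort P zero variance.* The text names no variance form. A pooled form gives about +1.8% to +62.9% for 11/34 vs 0/10, with no collapse.
- *That the interval would change the conclusion.* At 11/34 and 14/34 against 0/10, Wald, the score interval and CMH all exclude zero. Conflict at 0/10 needs 4 to 10 D responses of 34, below the expected range. At a P rate of 10% that is 0.349 × 0.403 = 14% of trials if the D rate is 33%, and 0.349 × 0.138 = 5% if it is 40%.
- *That the Clopper-Pearson interval and the difference interval contradict each other.* They estimate different quantities, and P's own uncertainty would appear in the same report.
- *That the unnamed strata are a design flaw.* With none assigned, the CMH test reduces to one stratum. This is a gap in wording.

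The score interval also has a limit: it does not adjust for two-stage stopping. Among stopped trials at a D rate of 33%, Miettinen-Nurminen covers 88% at a P rate of 20% and 55% at 30%. Such stops occur in about 11% and 3% of trials.

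**Conclusion.** The concern holds as a minor point about the interval method. Read as unpooled Wald, the planned interval is too narrow if the comparison is reported after a 0/10 stop: the limit nearer zero is 14 to 15 points too far from zero at the expected D counts (16.6 − 2.1 = 14.5; 24.6 − 10.6 = 14.0). Overall coverage is then 88.0-93.6% at D = 34, for D rates of 33-40% and P rates of 10-40%. The interval can also under-cover when cohort D is far below 34, even with 20 P patients. With 20 and 34 patients there is little to correct.

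These figures rest on the unpooled form, a two-sided 95% level, no continuity correction and, for overall coverage, reporting after a stop. The comparison is non-randomised, has no decision rule, and is not among the objectives or endpoints in 5.2 and 5.5. The primary decision on cohort P does not depend on it.

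**What to change.** In 10.3.3:

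1. Replace the normal-approximation interval with a two-sided 95% score interval. Miettinen-Nurminen is convenient because it agrees with the one-stratum CMH test without continuity correction: the two conflict in none of the 735 possible tables at 34 vs 20 and none of the 35 at 34 vs 0/10. Newcombe performs similarly.
2. Use it for any P-versus-D comparison of ORR or DCR, including one reported after a stop, and state the P and D counts analysed.
3. Label the comparison non-randomised and descriptive, and note that the interval does not adjust for two-stage stopping.
4. As a wording correction only, delete *stratified* from the CMH test, or name the strata in advance if any were intended.

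This costs three or four sentences and uses standard software. The downside is wider intervals at low P counts. At a D rate of 33% and D = 34, mean width after a 0/10 stop is 47.0 points against 31.1 for Wald; with 20 P patients and a P rate of 10% it is 44.3 against 42.1. At 11/34 vs 5/20 both are 49.3 points wide.
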